### **Study groups (random assignment)**

1. Manual positioning of body by nurse: left side, back, right side using positioning pillows;
2. Bed tilting: 15° lateral tilt, LINET Eleganza 5.

### **Study duration**

Start of study: January 2020

End of study: pilot study after recruitment of 50 patients. Complete study after recruitment of 200 patients.

## **Statistical Analysis Plan**

Running statistical analysis will be performed after recruitment of 50 patients. Ventilation distribution in lungs will be evaluated by EIT and in case of non-significant differences in detecting lung inhomogeneity and risk of pneumonia among group 1 and 2, the study will continue.

Complete study analysis will be performed after recruitment of 200 patients.

Continuous variables will be assessed using t-tests or Mann-Whitney tests depending on data distribution. Categorical variables will be assessed using chi-square tests. Multivariate logistic regression analysis will be used estimating the occurrence of pneumonia versus EIT related measures of lung inhomogeneity. For assessing the association between measured oxygenation, EIT derived parameters and ventilator parameters, the Pearson or Spearman correlation method will be used, depending on parameters' distribution.

Liberec, January 7th, 2020

[name]., Ph.D.

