### **Type of study**

1. Monocentric: Neurointensive Care Unit (NICU), Regional Hospital Liberec (research organization);
2. Prospective;
3. Randomized;
4. Intervention: parallel assignment;
5. Blind for statistics: statistics will only know type A or B randomization;
6. Patients: Pilot data in 50 patients, following a statistical evaluation, the study will continue with a total of 200 patients.

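### The rule for going past 50 patients is incomplete: it implies a possible stop on significance, conflicts with the stated continuation to 200, and comes with no error control

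*Combined protocol and SAP*

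**What the plan says.** The Statistical Analysis Plan schedules two analyses: "Running statistical analysis will be performed after recruitment of 50 patients", and "Complete study analysis will be performed after recruitment of 200 patients". Between them stands the continuation rule: "in case of non-significant differences in detecting lung inhomogeneity and risk of pneumonia among group 1 and 2, the study will continue". Nothing is written for the case where a difference is significant.

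Type of study, item 6, reads: "Pilot data in 50 patients, following a statistical evaluation, the study will continue with a total of 200 patients". An evaluation comes first, but continuing does not depend on its result. Study duration adds: "End of study: pilot study after recruitment of 50 patients. Complete study after recruitment of 200 patients". That may only mark the close of the pilot phase, and it gives no rule for choosing between the two ends.

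The rule names two outcomes. Pneumonia incidence is item 4 of the secondary aims. Lung inhomogeneity does not appear under The primary aim, which is collapse or atelectasis judged by EIT or chest radiograph.

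The tests are t-tests or Mann-Whitney tests for continuous data, and for the rest: "Categorical variables will be assessed using chi-square tests". No significance level, sidedness, interim threshold or final adjustment is given anywhere.

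**The concern.** A condition for continuing has little purpose unless something else can happen when it fails. The natural inference is that a significant result at 50 could end the study. If so, the first 50 patients are tested once at 50 and again within the 200, and nothing in the plan limits the combined chance of a false positive.

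Three things are at stake if the look can stop the trial. A positive result would not carry the error rate of a single test. An effect reported after a stop at 50 would be too large on average, because only large observed differences reach significance with so few patients. And pneumonia, a secondary aim, could end the trial before the primary aim is answered.

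If the look cannot stop the trial and supports no claim, none of this arises. The plan does not say which case applies.

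**Working it through.** **Inputs from the documents.** Looks at 50 and 200 patients (Statistical Analysis Plan); two parallel groups ("Intervention: parallel assignment", Type of study), with no allocation ratio given. The plan has no error-rate figure to reproduce.

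**Assumptions.** Two-sided 0.05 at each look, the same endpoint at both looks, and a constant allocation ratio. Simulated effect sizes also assume 1:1.

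**1. One endpoint, significance at 50 stops the trial with a claim.** The two test statistics have correlation √(50/200) = 0.5. With critical value 1.96 at both looks, the bivariate normal gives P(both significant) = 0.0093 under no effect. So

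P(either significant) = 0.05 + 0.05 − 0.0093 = 0.0907, about 9.1%.

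If the trial always runs to 200 and only that test counts, the figure is 5%. The two-look result scales with the assumed alpha: 1.9% at 0.01 and 17.6% at 0.10.

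**2. Either of two outcomes can stop at 50; one named endpoint is tested at 200.** For uncorrelated outcomes, the chance of any false claim is 1 − 0.95 × (1 − 0.0907) = 0.136. Simulation with 4 million draws per setting gives 13.6% at correlation 0 and 12.2% at 0.7.

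**3. Both outcomes must be significant to stop.** For uncorrelated outcomes, the final test contributes 0.05. The early stop adds 0.05 × (0.0907 − 0.05) = 0.002, giving 5.2%. Simulation gives 6.3% at correlation 0.7.

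**4. Binary endpoint.** Exact binomial enumeration at 25 then 100 per arm, assumed rates 10% to 50%:

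| Chi-square version | Two looks | One look at 200 |
|---|---|---|
| Uncorrected | 9.2% to 10.9% | 4.9% to 5.6% |
| Continuity-corrected | 3.0% to 6.7% | 2.5% to 4.0% |

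The corrected version exceeds 5% over two looks only from a rate of about 26%. The plan does not say which version it uses.

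**5. Exaggeration after a stop.** Simulated t-tests, true effect 0.4 SD: the trial stops at 50 with probability 28%. The mean observed effect among those stops, in whichever direction, is 0.73 SD. Mean enrolment is 0.283 × 50 + 0.717 × 200 = about 158.

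**6. A boundary that holds 5%.** Requiring p<0.001 at 50 and p<0.049 at 200, with correlation 0.5, gives 4.96% overall.

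**The case against.** The sections can be read together. Type of study gives the outline, the Statistical Analysis Plan supplies the criterion, and Study duration labels the 50-patient point a pilot. On that view the rule is under-specified rather than contradicted, and no sentence says that significance stops the trial or supports a claim.

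Much of this stands. A reader might infer that the plan allows continuation only after non-significance, or that it promises 200 whatever the data show. The documents contain neither statement: the first is implied by the conditional wording, the second by the absence of a condition. A reader might also infer that this trial has a 9.1% error rate. That is not supported either. The figure needs a stop with a claim, an alpha the plan never states, and the same endpoint at both looks. The last is itself in doubt, because lung inhomogeneity is not worded as the primary aim. If the two differ, 9.1% is not the primary endpoint's error rate.

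The objection does not remove the gap. Even read together, the sections leave the action after significance open, do not say whether one or both outcomes decide, and set no alpha or boundary. Nor do they show which section reflects the sponsor's intent, so the remedy should not choose for the sponsor.

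**Conclusion.** The concern holds as a defect in the continuation rule. The Statistical Analysis Plan implies a possible stop that Type of study does not provide for, and the significant branch and the error control are both missing. The consequence depends on the rule the sponsor intends, under the assumptions listed above:

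- always to 200, with only that analysis confirmatory: 5%, no inflation;
- a stop with a claim on the same endpoint: about 9.1%;
- either outcome can stop: about 12% to 14% for any false claim;
- both needed to stop: about 5.2% to 6.3%.

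For a binary endpoint the size also depends on the chi-square version, and with the continuity correction there may be no excess over 5%. It is certain that the sections need reconciling. How far the error rate is affected is not.

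**What to change.** Rewrite the continuation rule in the Statistical Analysis Plan in one of two ways.

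**(a) To agree with Type of study.** State that the 50-patient look is non-binding for efficacy and supports no efficacy claim, that the trial continues to 200, and that only the 200-patient analysis is confirmatory, at a stated two-sided alpha.

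**(b) If an early efficacy stop is intended.** Define one primary endpoint from The primary aim (EIT, chest radiograph, or a stated way of combining them). Use it at both looks with a boundary that holds 5% overall, for example p<0.001 at 50 and p<0.049 at 200. Amend item 6 of Type of study to match.

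In both cases pneumonia should not be an efficacy trigger. If it is meant as a safety review, say so and keep it separate from efficacy.

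**Cost.** A few lines of text; the maximum stays at 200. Option (a) gives up an early efficacy stop: at a true 0.4 SD, mean enrolment is 200 rather than about 158 with two unadjusted looks, and power is 1.6 points lower (80.3% against 81.9%), the extra power having come from the uncontrolled error rate. Option (b) makes an early stop rare, with probability 0.4% to 10% for true effects of 0.2 to 0.6 SD. Over that range it costs at most about 0.3 points of power against a single test at 200.

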### **Study Objectives**

Prevention of lung inhomogeneity is an essential part of preventive strategy in neurocritical care, reducing the risks of secondary brain damage from hypoxemia, hypo/hypercapnia or pneumonia. The investigators will examine the effect of lateral tilting (routinely used in critical care) on the lung inhomogeneity that will be analyzed by electrical impedance tomography (EIT). Two types of lateral tilting will be compared: manual positioning of body by nurse versus the bed tilting (15° lateral tilt, original company name (LINET) and product brand name Eleganza 5).

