### **Exclusion criteria**

1. Intracranial hypertension;
2. History of primary lung disease;
3. The terminal stage of the disease;
4. Refractory hemodynamic instability.

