### **The primary aim**

Atelectasis/collapse assessed by EIT or chest x-ray (CXR) at end of observation period.

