### **The secondary aims**

1. Evaluating oxygenation parameters;
2. Evaluating hemodynamic parameters: stroke volume variation (SVV) and cardiac index (CI) in one type of hemodynamic monitor;
3. Comparing staying in Neurocenter Neurointensive Care Unit and cost effectiveness between two groups;
4. Profiling pneumonia incidence between two groups.

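### Does the pneumonia regression need a rule that the EIT recording comes before pneumonia onset?

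*Combined protocol and SAP*

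**What the plan says.** The Statistical Analysis Plan gives this model one sentence: "Multivariate logistic regression analysis will be used estimating the occurrence of pneumonia versus EIT related measures of lung inhomogeneity". It names no recording, no time order and no covariates. The section's other sentence about EIT assessment, "Ventilation distribution in lungs will be evaluated by EIT", belongs to the look at 50 patients and gives no time either.

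Other sections bear on the point but do not settle it:

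- **The primary aim** holds the only timed EIT in the documents: "Atelectasis/collapse assessed by EIT or chest x-ray (CXR) at end of observation period". That time is attached to the primary outcome, not to the pneumonia model, and the length of observation is not given.
- **The secondary aims** list "Profiling pneumonia incidence between two groups". Incidence normally means new cases, but no onset rule or window follows.
- **Exclusion criteria** list "History of primary lung disease". Pneumonia present at entry is not named.
- **Study Objectives** describe preventing lung inhomogeneity as an "essential part of preventive strategy in neurocritical care, reducing the risks of secondary brain damage from hypoxemia, hypo/hypercapnia or pneumonia".

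**The concern.** Pneumonia is the modelled outcome and EIT inhomogeneity the explanatory measure, so a positive odds ratio invites the reading that inhomogeneity leads to pneumonia. The rationale in Study Objectives encourages that reading. Pneumonia can itself disturb the distribution of ventilation. If the recording comes from the close of observation and some pneumonias began before it, part of the odds ratio runs from pneumonia to EIT. A model with no true predictive content could then give a significant result, and the report could present inhomogeneity as a risk factor on that basis. Only the conclusion from this one secondary model would be affected.

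**Working it through.** **The plan's own figures.** There is none to reproduce. Type of study gives the numbers ("Pilot data in 50 patients, following a statistical evaluation, the study will continue with a total of 200 patients") without a pneumonia rate, effect size, SD or power, and no odds ratio is stated. Only n = 200 below comes from the documents; every other input is an assumption.

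**Assumed inputs**

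- EIT inhomogeneity is a score with SD 1.
- OR0 is the true odds ratio per SD of EIT before onset: 1.0 or 1.5.
- f is the share of pneumonias that began before the recording used: 0 to 1.
- d is the rise in the score caused by pneumonia: 0.3 to 0.8 SD.
- ρ is the correlation between earlier and late EIT: 1.0 or 0.5.
- The pneumonia rate is 10% to 30%.

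**Approximation.** For a roughly normal score, the fitted log odds ratio per SD is close to the difference in mean score between patients with and without pneumonia:

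ln(OR fitted) ≈ ρ × ln(OR0) + f × d

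The first term is the true association, weakened if late EIT is a poor stand-in for earlier EIT. The second is the reverse effect.

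**Step 1: no true effect (OR0 = 1, so the first term is 0).**

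| Share preceding, f | Formula, d = 0.3 to 0.8 | Simulated median odds ratio | p < 0.05 |
|---|---|---|---|
| 0 | exp(0) = 1.00 | 0.99–1.01 | 4–6% |
| 0.10 | exp(0.03) = 1.03 to exp(0.08) = 1.08 | 1.02–1.09 | 5–8% |
| 0.25 | exp(0.075) = 1.08 to exp(0.20) = 1.22 | 1.07–1.22 | 7–25% |
| 0.50 | exp(0.15) = 1.16 to exp(0.40) = 1.49 | 1.16–1.49 | 9–71% |
| 1.00 | exp(0.30) = 1.35 to exp(0.80) = 2.23 | 1.35–2.26 | 23–100% |

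The simulations used 3,000 trials per cell and one EIT score without covariates, whereas the plan says the model is multivariate.

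**Step 2: a true odds ratio of 1.5 (ln 1.5 = 0.405).**

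- ρ = 1, f = 0.5, d = 0.8: exp(0.405 + 0.40) = 2.24 (simulated 2.21 at a 20% rate). This is inflation.
- ρ = 0.5, f = 0: exp(0.5 × 0.405) = 1.22 (simulated 1.21). This is attenuation.
- ρ = 0.5, f = 0.1, d = 0.3 to 0.8: exp(0.203 + 0.03) = 1.26 to exp(0.203 + 0.08) = 1.33 (simulated 1.26–1.32).
- ρ = 0.5, f = 0.25, d = 0.3 to 0.8: exp(0.203 + 0.075) = 1.32 to exp(0.203 + 0.20) = 1.50 (simulated 1.31–1.48).

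The two terms cancel when f × d = (1 − ρ) × 0.405. At ρ = 0.5 that is 0.203, so with half the pneumonias preceding, d must exceed 0.203 / 0.5 = 0.41 SD before the fitted value passes 1.5. Inflation above the truth therefore needs either stable EIT or a large share of early pneumonias with a sizeable shift.

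**Step 3: what a strict time-order rule would cost.** Take a 20% rate, so 200 × 0.20 = 40 events, with OR0 = 1.5. Removing 10%, 25% or 50% of events leaves 36, 30 or 20, and simulated power falls from 60% to 57%, 50% or 38%. Those figures assume that the early recording measures the relevant inhomogeneity perfectly. If late inhomogeneity is what matters and the early recording correlates 0.7 with it, power is 33%, or 27% with a quarter of events removed. At a correlation of 0.5 it is 19%, or 16%.

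**The case for a change.** The best case for a change is that closing such choices before the data are seen is what a SAP is for, and that two or three sentences would do it. One recording could be named for every patient and only later pneumonia counted or, failing that, the model could be labelled cross-sectional. Nothing elsewhere in the document supplies the order, and the exclusions would not remove pneumonia present at entry. With no true effect there is nothing to attenuate, so the only possible distortion is upward.

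Much of this stands. The text is silent, the arithmetic holds, and a predictive claim drawn from a late recording would be unsound. The case for amending the plan is weaker, for three reasons.

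1. The harm requires a claim the plan does not make. The model sets pneumonia against EIT measures and is followed by a correlation analysis expressly about association. None of the listed aims asks whether inhomogeneity predicts pneumonia; the pneumonia aim compares the arms. The sentence in Study Objectives concerns secondary brain damage, with pneumonia as one of its sources, and is background rather than a hypothesis for this model.
2. The strict rule is a trade-off, not a clear gain. No section shows that an early EIT or onset dates are held, though the site may have them. An early recording also reflects less of the positioning period that the trial studies, and it does not remove pneumonia that is developing but not yet diagnosed.
3. The label-only remedy changes no estimate, test or decision. It asks for care in wording that a competent report would show anyway.

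**Conclusion.** No change to the plan follows. The time order is unstated, not wrong, and this is a gap that analysts can fill sensibly by saying which recording was used and reporting the odds ratio as an association. Read that way, the estimate is valid whichever recording is chosen.

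The possible distortion of a predictive reading runs from none to large. With no true effect the median odds ratio is 0.99 to 2.26 per SD and the rejection rate 4% to 100%. With a true value of 1.5, the cases worked above run from 1.22 to 2.24 by the formula. These figures rest on assumed pneumonia rates, shares, shifts and correlations, and on a single-score model. The documents give nothing to choose among them, so they fix neither the size nor the net direction.

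The conclusion would differ if the plan had named prediction of pneumonia as an aim, or if the model fed the continuation decision at 50 patients. Neither is the case: that decision rests on differences between the two groups.
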